11.8 Safety Analysis

Adverse events will be classified using standard Medical Dictionary for Regulatory Activities (MedDRA) terminology Version 20.0 or higher and summarized by treatment group. Summary tables comparing the type, date of onset, date of resolution, incidence, severity, relationship to the study product, action taken, and outcome will be prepared by treatment group. If sufficient data exist, then AE frequencies will be compared among treatments using Fisher's exact test or a similar test. Application site reactions and ocular discomfort will be compared descriptively among treatment groups.

Concomitant medication use during the randomized treatment period will be tabulated by patient.

Signs and symptoms of head lice will not be considered AEs, unless in the Investigator's opinion, they have increased in frequency and/or severity to such an extent that the Investigator/patient considers to be clinically significant.

All patients who received randomized treatment and received study product will be included in the comparative safety analysis.

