2. OBJECTIVES

The objectives of this study are to:

1. Evaluate the therapeutic equivalence of the Test formulation, Ivermectin Lotion 0.5% (Actavis Laboratories UT, Inc.) to the Reference product, SKLICE® (ivermectin) Lotion, 0.5% (Arbor Pharmaceuticals, LLC) in the treatment of active head lice infestation.
2. Demonstrate the superiority of the Test and Reference (active) treatments over Placebo treatment in patients with active head lice infestation.
3. Compare the safety of Test, Reference and Placebo treatments in patients with active head lice infestation.

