8. STATISTICAL ANALYSIS METHODS

If not otherwise specified, statistical significance is defined as $p < 0.05$ and is two-tailed. Data will be summarized with respect to demographic and baseline characteristics, efficacy variables and safety variables.

For categorical variables, the number and percent of each category within a parameter will be calculated for non-missing data. For continuous variables, statistics will include number of observations, mean, standard deviation, median, minimum and maximum values.

All statistical analyses will be conducted using SAS[®], Version 9.4 or higher. Datasets will be prepared using headings from Clinical Data Interchange Consortium (CDISC) Study Data Tabulation Model (SDTM) implementation for human clinical trials and ADaM (Analysis Dataset Model). ADaM datasets will include but not limited to ADSL, ADEFF, ADAE, ADVS, ADCM and ADMH.

STATISTICAL ANALYSIS PLAN

Ivermectin Lotion 0.5%

Protocol / Study No. 71691702

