8.3.1 Adverse Events

All the adverse events (AEs) reported throughout the study will be coded and classified according to the MedDRA (Medical Dictionary for Regulatory Activities) coding dictionary (Version 20.0 or higher). Each adverse event is to be evaluated for date of start and end, seriousness, severity, causal relationship with the study drugs, action taken and outcome.

The total number and percentage of patients with at least one AEs, discontinued study drug due to AEs, AE severity and AEs related to investigational product, serious AEs and death will be summarized by treatment groups.

A summary table of the number and percent of patients with AEs by system organ class, preferred term, and treatment group will be presented. Each patient will be counted only once within each preferred term.

A frequency summary table of the number of AEs by system organ class, preferred term, severity, and treatment group will be presented. Severity will be classified as “Mild”, “Moderate”, or “Severe”.

Similarly, a frequency summary table of the number of AEs by system organ class, preferred term, and relationship to a study drug, and treatment group will be presented. Relationship to a study drug will be classified as “Related” or “Not Related”.

Adverse event frequencies will be compared between treatments using Fisher’s exact test. If the overall Fisher’s test is statistically significant, a pairwise test will be conducted for Test and Reference to determine if the difference in AEs is related to the active product.

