8.4 Multiple Comparisons

No multiple comparison adjustment will be made in this study.

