Placebo: Placebo (vehicle) lotion (Actavis Laboratories UT, Inc.)

OUTPUT: L:\DEV\917\71691702\SAS\OUT\XXXX

Created on: ddmmmyy hh:mm

Page 1 of N

STATISTICAL ANALYSIS PLAN

Ivermectin Cream 0.5%

Protocol / Study No. 71691702

T16.1.9.10 Summary of Frequency of All Adverse Events by Body System (Safety Population)

Body System	MedDRA Term	Test (N = xxx)		Reference (N = xxx)		Placebo (N = xxx)		Fisher's P-value
		Events	Patients	Events	Patients	Events	Patients	
Patient with at least one AE	Total	xx	xx (xx.x%)	xx	xx (xx.x%)	xx	xx (xx.x%)	x.XXXX
Ear and labyrinth disorders	Ear pain	xx	xx (xx.x%)	xx	xx (xx.x%)	xx	xx (xx.x%)	x.XXXX
	etc.							
	etc.							

Comparison of treatment groups is with respect to the number of patients with at least one occurrence of the AE.

Test: Ivermectin Lotion, 0.5% (Actavis Laboratories UT, Inc.)

Reference: SKLICE® (ivermectin) Lotion, 0.5% (Arbor Pharmaceuticals, LLC)

Placebo: Placebo (vehicle) lotion (Actavis Laboratories UT, Inc.)

OUTPUT: L:\DEV\917\71691702\SAS\OUT\XXXX

Created on: ddmmmyy hh:mm

Page 1 of N

STATISTICAL ANALYSIS PLAN

Ivermectin Cream 0.5%

Protocol / Study No. 71691702

T16.1.9.11 Summary of Frequency of All Adverse Events by Severity (Safety Population)

Body System	MedDRA Term	Test			Reference			Placebo		
		# Events			# Events			# Events		
		(N=xx)			(N=xx)			(N=xx)		
Total AEs	Total AEs	xx(xx.x%)	xx(xx.x%)	xx (xx.x%)	xx(xx.x%)	xx(xx.x%)	xx (xx.x%)	xx (xx.x%)	xx (xx.x%)	xx (xx.x%)
Ear and labyrinth disorders	Ear pain	xx(xx.x%)	xx(xx.x%)	xx (xx.x%)	xx(xx.x%)	xx(xx.x%)	xx (xx.x%)	xx (xx.x%)	xx (xx.x%)	xx (xx.x%)
	Hypoacusis	xx(xx.x%)	xx(xx.x%)	xx (xx.x%)	xx(xx.x%)	xx(xx.x%)	xx (xx.x%)	xx (xx.x%)	xx (xx.x%)	xx (xx.x%)

etc.

N = Total number of events in each treatment group; Percentage is based on total number of events.

Test: Ivermectin Lotion, 0.5% (Actavis Laboratories UT, Inc.)

Reference: SKLICE® (ivermectin) Lotion, 0.5% (Arbor Pharmaceuticals, LLC)

Placebo: Placebo (vehicle) lotion (Actavis Laboratories UT, Inc.)

OUTPUT: L:\DEV\917\71691702\SAS\OUT\XXXX

Created on: ddmmmyy hh:mm

Page 1 of N

STATISTICAL ANALYSIS PLAN**Ivermectin Cream 0.5%****Protocol / Study No. 71691702****T16.1.9.12 Summary of Frequency of All Adverse Events by Relationship
(Safety Population)**

Body System	MedDRA Term	Test		Reference		Placebo	
		# Events		# Events		# Events	
		Related	Not Related	Related	Not Related	Related	Not Related

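### The plan's only inferential rule for adverse events is a gated three-arm Fisher p-value; no Test minus Reference difference or confidence interval is planned

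*SAP*

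**What the plan says.** SAP section 2 gives objective 3 as "Compare the safety of Test, Reference and Placebo treatments in patients with active head lice infestation"; Protocol 9.0 has the same objective. No hypothesis or margin is attached to it.

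SAP 8.3.1 supplies the inference. AE frequencies go first into a Fisher's exact test across all three arms. The second step is conditional: when that overall "test is statistically significant, a pairwise test will be conducted for Test and Reference". Its declared purpose is to judge whether a difference comes from the active ingredient. The default level applies: "statistical significance is defined as $p < 0.05$ and is two-tailed" (SAP 8). SAP 8.4 adds: "No multiple comparison adjustment will be made in this study".

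Protocol 11.8 is looser and has no gate: "If sufficient data exist, then AE frequencies will be compared among treatments using" Fisher's exact or a similar test.

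Shell T16.1.9.10 has events, patients and percentages for each arm, and one Fisher p-value per row. Its footnote reads: "Comparison of treatment groups is with respect to the number of patients with at least one occurrence of the AE". It has no column for a difference or an interval. Other shells tabulate severity, relationship and serious events by arm. SAP 8.3.2 compares application site reactions and ocular discomfort descriptively.

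**The concern.** For a generic product, Test against Reference is the safety contrast that matters most. Under SAP 8.3.1 it is tested only after a different test, the three-arm one, has reached significance. A p-value of 0.05 or more cannot separate similar AE rates from too few events to tell, and the plan provides nothing else that would. The efficacy comparison of the same two products in SAP 8.2.1 does report a difference with a 90% interval.

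The trial is sized on the efficacy endpoint (SAP 5), so the Fisher test has whatever power for AEs that size happens to give. At stake is whether the study report can say what excess of AEs on the generic is still compatible with the data.

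**Working it through.** **Inputs from the documents.** About 378 index patients (Protocol synopsis; SAP 5 has about 364, from the protocol before its amendment). The Safety population is everyone randomized who received product, so it includes non-index patients. Exclusion criterion 4 caps infested household members at three, so the upper bound is 3 × 378 = 1,134. Two-sided 0.05, no multiplicity adjustment. No power is stated for any safety comparison, so there is no plan figure to reproduce; 378 itself cannot be rebuilt because its assumptions are redacted.

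**Assumptions.** Allocation is redacted; I take 1:1:1, with 2:2:1 and 3:3:1 as checks. AE rates are not given; I take Reference rates of 2% to 20%, Placebo equal to Reference, and Test at twice Reference. Patients are treated as independent. Per-arm sizes are 378/3 = 126 (index only), 252 (two per household, assumed) and 378 (upper bound).

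**Step 1: detection under the gated rule.** I enumerated three independent binomials exactly. The rule flags Test when the three-arm exact Fisher p is below 0.05, the Test–Reference exact Fisher p is below 0.05, and Test is the higher arm.

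| Reference → Test | 126 per arm | 252 per arm | 378 per arm |
|---|---|---|---|
| 2% → 4% | 6.2% | 15.4% | 25.9% |
| 5% → 10% | 21.1% | 47.4% | 67.8% |
| 10% → 20% | 50.5% | 85.1% | 96.4% |
| 15% → 30% | 75.8% | 97.6% | not run |
| 20% → 40% | 91.3% | not run | not run |

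For 5% → 10% the miss rates are 100 − 21.1 = 78.9%, 100 − 47.4 = 52.6% and 100 − 67.8 = 32.2%. A separate simulation (800 to 2,000 replicates per case) gave 79%, 52% and 31%, within simulation error. With 378 patients allocated 2:2:1 (151/151/76), detection of 5% → 10% is 25.9%; with 3:3:1 (162/162/54) it is 27.7%.

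With equal allocation, a doubling is missed more often than not when the Reference rate is below about 10% (378 patients in all), a little above 5% (756) or between 3% and 5% (1,134; at 3% → 6% detection is 40.8%).

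**Step 2: how much is due to the gate.** For 5% → 10%, the Test–Reference test with no gate detects 23.7%, 51.6% and 70.8%. The gate therefore costs 23.7 − 21.1 = 2.6, 51.6 − 47.4 = 4.2 and 70.8 − 67.8 = 3.0 points. The rest is sample size.

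**Step 3: a worked example.** Take 11/126 on Test, 5/126 on Reference and 5/126 on Placebo. The overall p is 0.21, so no pairwise test is run. The difference is 8.73% − 3.97% = 4.8 points. Its standard error is √(0.0873 × 0.9127/126 + 0.0397 × 0.9603/126) = 0.0306, so the 95% interval is 4.8 ± 1.96 × 3.06, or −1.2 to +10.8 points. With 5/126 in the other two arms, Test must reach 15/126, an observed tripling, before both tests are significant (overall p = 0.024, pairwise p = 0.034). At 13/126 the overall p is 0.070 and the gate stays shut.

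**Step 4: what an interval would show.** The half-width is 1.96 × √(pT(1 − pT)/n + pR(1 − pR)/n).

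- Both rates 5%: ±5.4, ±3.8 and ±3.1 points at 126, 252 and 378 per arm.
- 10% against 5%: ±6.5, ±4.6 and ±3.7 points, so the expected upper limits are about +11.5, +9.6 and +8.7 points.

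These intervals make visible that a doubling is not excluded. Household members share an arm (SAP 4), so with more than one patient per household, positive within-household correlation would widen them and raise the miss rates.

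**The case against.** The strongest reply is that safety here is descriptive. Objective 3 sets no hypothesis, equivalence is declared on the primary efficacy endpoint alone, and T16.1.9.10 puts Test and Reference side by side with counts and percentages whatever the p-value. A reader could work out a crude difference and interval from it. With many preferred terms and no multiplicity adjustment, testing overall before pairwise is a defensible way to limit false alarms. In the 11/5/5 example the gate hides nothing: the ungated pairwise p is 0.195 and the interval includes zero.

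Much of that stands, and it rules out four stronger readings that a reader might infer:

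- *Test and Reference are not compared at all when the gate stays shut.* They are still tabulated together; only the test is withheld.
- *A non-significant result counts as no difference.* Neither document says so, and there is no pass/fail rule for safety.
- *The trial cannot answer objective 3.* It can describe AEs by arm. It lacks a planned measure of the uncertainty in the contrast.
- *A doubled rate would usually be missed.* That depends on a Reference rate and a safety sample size that the documents do not give. With 126 per arm, a doubling from 15% or 20% is usually detected; with 252 or more, so is a doubling from 10%.

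The reply does not supply the missing estimate. Leaving each reader to derive an interval from a table is not a plan, and a simple binomial interval would ignore the shared household arm.

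**Conclusion.** The point holds in a limited form. The gated Fisher p-value is the only inferential rule for AEs, and no effect estimate or interval is planned for any AE contrast. When the overall test is not significant, the planned output does not state how large a Test–Reference excess remains possible.

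As to size, the rule misses a doubling from 5% to 10% about 79%, 53% and 32% of the time at 126, 252 and 378 per arm. This assumes equal allocation, independent patients and Placebo equal to Reference. The rule is weaker for rarer terms and adequate at higher rates. The gate accounts for only about 3 to 4 points of this. The missing estimate and interval are the main defect; the gate is secondary, but it serves little purpose once intervals are reported. Neither the equivalence nor the superiority conclusion is affected, so this is a change that should be made rather than one the trial depends on.

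**What to change.** In SAP 8.3.1, remove the condition that the overall Fisher test be significant. Protocol 11.8 contains no such condition, so its text need not change. State instead that, whatever the p-value:

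- The Test minus Reference difference, and each active minus Placebo, in the proportion of patients will be reported for any AE, any related AE, and each preferred term above a frequency threshold fixed before unblinding.
- Each difference will carry a two-sided 95% confidence interval whose variance allows for household members sharing an arm.
- A non-significant p-value will not be taken as evidence of comparable safety.

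Add difference and interval columns to T16.1.9.10 and keep the Fisher p-value there as descriptive. Add a patient-level row for any related AE, because T16.1.9.12 counts events only.

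The cost is SAP wording, changes to the shells and some programming for the clustered variance; no new data and no more patients. The drawback is more intervals to read, unadjusted for multiplicity and some of them wide. The change does not raise the power to detect an excess; it reports what the data cannot rule out.

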3. OVERALL STUDY DESIGN

This randomized, double-blind, placebo-controlled, parallel-design, multiple-site clinical study has been designed to evaluate the efficacy and safety of a generic Ivermectin Lotion 0.5% (Actavis Laboratories UT, Inc.) compared to the Food and Drug Administration (FDA) Reference Listed Drug (RLD) SKLICE® (ivermectin) Lotion, 0.5% (Arbor Pharmaceuticals,

STATISTICAL ANALYSIS PLAN

Ivermectin Lotion 0.5%

Protocol / Study No. 71691702

LLC) in patients with active head lice infestation. Additionally, both the Test and Reference (i.e., the RLD) treatments will be tested for superiority to a Placebo.

Before any study-specific procedures are performed, all patients will read and sign the IRB-approved informed consent form (ICF). In addition, patients who are considered minors in the state the study is being conducted (< 18 years of age in most states), must have a signed parental/guardian ICF, indicating approval to participate, as well as a signed assent to participate form, as appropriate. Patients 11-17 years of age will read and sign an IRB-approved assent form and patients 6-10 years of age will provide verbal assent. Patients 6 months-5 years of age will be exempt from providing assent based on the child's comprehension and cognitive skills.

Males and females, 6 months of age and older with an active head lice infestation will be randomized [REDACTED] to one of the three study products as follows:

- **Test:** Ivermectin Lotion, 0.5% (Actavis Laboratories UT, Inc.)
- **Reference:** SKLICE® (ivermectin) Lotion, 0.5% (Arbor Pharmaceuticals, LLC)
- **Placebo:** Placebo (vehicle) lotion (Actavis Laboratories UT, Inc.)

Patients, [REDACTED] will be instructed to administer a single application of the study product to the hair on the day of or the day after enrollment into the study, leave the study product on the hair and scalp for 10 minutes, and then rinse off with warm water. Patients and infested household members will be instructed to apply the study product at home. The day of dosing will be considered Day 1.

Patients will attend the following four scheduled clinic visits:

- Visit 1 (Day -1 to 1): Screening/Baseline
- Visit 2 (Day 2): Interim Visit
- Visit 3 (Day 8 ± 2): Interim Visit
- Visit 4 (Day 15 ± 2): End of Study

At Visit 2 (Day 2), [REDACTED] enrolled [REDACTED] will return the study product to the clinic. Visit 2 must occur the day after dosing. [REDACTED]

At

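### The follow-up adverse event test compares two ivermectin products, so it cannot show whether an excess over Placebo is related to the active

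*SAP*

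**What the plan says.** SAP 8.3.1 has two steps. First, "Adverse event frequencies will be compared between treatments using" Fisher's exact test. If that overall test is significant, "a pairwise test will be conducted for Test and Reference to determine if the difference in AEs is related to the active product". No other pairwise AE comparison is named.

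Shell T16.1.9.10 sets out Test, Reference and Placebo with one Fisher p-value per row. Its footnote fixes the counting unit: "Comparison of treatment groups is with respect to the number of patients with at least one occurrence of the AE". It has no column for a pairwise p-value.

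SAP section 3 lists the arms. Test and Reference are each ivermectin lotion at 0.5%. Placebo is a vehicle lotion from the Test manufacturer.

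Protocol 11.8 says only that AE frequencies are compared among treatments if there are enough data, and gives no pairwise rule. The third study objective in both documents is a safety comparison across all three arms. On multiplicity, SAP 8.4 states: "No multiple comparison adjustment will be made in this study".

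**The concern.** The rule gives one test a purpose that the test cannot serve. Whether an AE excess comes from ivermectin is a question about arms with ivermectin against an arm without it. Two arms with the same active at the same strength differ only in the remaining formulation and the manufacturer.

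The rule can therefore mislead in both directions. If ivermectin raises an AE equally in both active arms, the expected follow-up result is null, and the purpose sentence invites the reader to conclude that the active is not involved. If only one product raises the AE, the follow-up tends to be significant, and the same sentence invites the reader to call a product difference an ivermectin effect. At stake is how a safety signal is interpreted; the equivalence and superiority conclusions do not depend on it.

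**Working it through.** **Nothing to reproduce.** The SAP gives no rate, power or sample size for the AE comparison. The logical point needs no numbers. The calculation below only shows how often the rule would mislead.

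**Inputs**
- Rule: SAP 8.3.1, an overall test across three arms, then Test vs Reference if significant.
- Level: 0.05 two-sided, the general default in SAP section 8; no adjustment (SAP 8.4).
- Unit: patients with at least one occurrence (T16.1.9.10).
- Size: about 378 index patients (Protocol synopsis). The allocation ratio is redacted, so two are assumed: 378/3 = 126 per arm, and 2:2:1, which gives 151/151/76.
- AE rates: assumed, because the documents give none.

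**Formulas.** With m affected patients among N in total, the three-arm exact (Freeman-Halton) probability of a table (a, b, c) is C(n1,a)·C(n2,b)·C(n3,c)/C(N,m). The p-value sums the probabilities of all tables no more likely than the one observed. The pairwise test is the same with two arms.

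**Worked examples**
- 12/126, 12/126, 1/126: overall p = 0.002; Test vs Reference p = 1.0; Test vs Placebo p = 0.003.
- 25/126, 25/126, 6/126: overall p = 0.0002; Test vs Reference p = 1.00; each active vs Placebo p = 0.0004.
- 30/151, 30/151, 4/76: overall p = 0.005; Test vs Reference p = 1.0; each active vs Placebo p = 0.003.

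Equal counts in equal-sized arms give the most likely two-arm table, so p = 1 whatever Placebo shows.

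**Simulation of the rule** (10,000 trials per row). The last three columns are the share significant among trials where the overall test was significant.

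| True rates, Test/Ref/Placebo | Arm sizes | Overall p < 0.05 | Test vs Ref | Test vs Placebo | Ref vs Placebo |
|---|---|---|---|---|---|
| 10/10/2% | 126 each | 82% | 3.4% | 84% | 83% |
| 15/15/5% | 126 each | 79% | 4.3% | 85% | 84% |
| 20/20/5% | 126 each | 98% | 3.4% | 97% | 96% |
| 30/30/10% | 126 each | 99% | 3.5% | 98% | 98% |
| 10/10/2% | 151/151/76 | 61% | 5.1% | 86% | 85% |
| 15/15/5% | 151/151/76 | 62% | 5.3% | 86% | 86% |
| 20/20/5% | 151/151/76 | 91% | 3.9% | 95% | 95% |
| 30/30/10% | 151/151/76 | 96% | 4.0% | 97% | 97% |
| 15/5/5% | 126 each | 80% | 86% | 85% | 2.4% |
| 15/5/5% | 151/151/76 | 84% | 93% | 71% | 4.2% |
| 10/10/10% | 126 each | 5% | 38% | 43% | 48% |

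At 10/10/1% with 126 per arm, the overall test is significant in about 95% of trials. In those, Test vs Reference is significant in about 3%, and at least one active vs Placebo in nearly all.

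**Reading**
- Rows 1-8, equal effect in both actives: Test vs Reference is significant in 3.4-5.3% of triggered trials, so it is null in 94.7-96.6%. With the 10/10/1% case (about 97% null), the range is about 95-97%.
- Rows 9-10, only Test raised: the follow-up is significant in 86-93% of triggered trials, although the AE is no more frequent on Reference than on Placebo.
- Row 11, no effect at all: the overall test rarely triggers, and the follow-up is significant in 38% of those triggers. The 95-97% therefore applies when there is a clear excess, and should not be carried over to rare or weak effects.

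**The case against.** **The stronger reading.** A reader might infer that the SAP would report a true drug effect as not drug related. The documents do not support that. SAP 8.3.1 gives no wording for a null follow-up, and relatedness is assigned elsewhere: the investigator judges each event (Protocol 10.7 and 10.7.5), and the result is tabulated by arm in T16.1.9.12. Nothing lets the Fisher follow-up override that judgement. T16.1.9.10 also prints all three arms beside the overall p-value, so in the first worked example 12, 12 and 1 of 126 with p = 0.002 would be seen together. This objection stands, and it limits the consequence to a possible misreading.

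**Other readings of the sentence.** The protocol uses *active* for both the Test and Reference products (8.4, 10.1), so the authors may have meant to ask whether the difference lies between the two. That is a sensible question for a generic, but it is not what the purpose clause says, and the sentence would still need rewording. Alternatively, a test *for* Test and Reference could mean each against Placebo. The singular *a pairwise test* fits that poorly.

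**Low stakes and assumed rates.** AE testing is supportive, and Protocol 11.8 makes it conditional on sufficient data. Protocol 8.5 calls the potential for significant drug-related side effects low. With 126 per arm, rates of 5/5/2%, 3/3/1% and 2/2/0.5% trigger the overall test in only about 19%, 12.5% and 7% of trials, so the rule may seldom come into play. The simulation also counts index patients only. The Safety population adds non-index patients, who share an arm within a household (SAP section 4), and that clustering is ignored. All of this bears on how often the problem arises, not on whether the contrast can answer its question.

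**Limits of the remedy.** Placebo comes from the Test manufacturer, and the documents do not say that Reference has the same excipients. Reference vs Placebo may therefore mix active and vehicle effects. This stands and shapes the fix.

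**Conclusion.** The point holds as a fault in the stated rule. The only named follow-up cannot answer the question set for it, because both arms contain ivermectin 0.5%, and neither the SAP text nor a shell adds an active-vs-Placebo AE test. That conclusion rests on the arm definitions alone.

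The size rests on assumptions. With equal and clearly raised rates in both actives, and 126 per arm or a 2:2:1 split, the follow-up is null in about 95-97% of triggered trials. If only Test is raised, it is significant in 86-93%. Rarer events would trigger the rule less often.

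The harm is a possible misinterpretation in either direction. It is not a hidden signal or a pre-scripted wrong conclusion, and efficacy is unaffected. The sentence is wrong as written and should be corrected.

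**What to change.** Revise SAP 8.3.1 before database lock, while the blind is intact:

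1. After a significant overall Fisher test, compare Test vs Placebo and Reference vs Placebo.
2. Name Test vs Placebo as the main contrast for relation to the active, because both products come from the same manufacturer. Read Reference vs Placebo as a product-vs-vehicle comparison.
3. Keep Test vs Reference, labelled as a product (formulation) difference.
4. Reword the purpose sentence so that each contrast carries only its own interpretation and the three are read together. A null result should not be presented as evidence of no relation to the active.
5. Add the pairwise p-values to T16.1.9.10.

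This needs no new data and no change in study conduct. The cost is some SAP wording, extra table columns and two more exploratory p-values for each AE row that passes the overall test. They would be unadjusted, in line with SAP 8.4, and should be labelled as such.
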